
3.7. Stratification

Throughout the study, we will stratify by menthol status (no required sample size) and age range (no required sample size 18-24/25+). We recognize that it will likely be more challenging to recruit young adults. We will make use of targeted recruitment strategies (e.g., social media for the recruitment of young adults).

4. Baseline Visit

4.1. Baseline Visit Scheduling Requirements

Participants will return for a baseline visit one week after their screening visit. The ideal visit window is 6-10 days, but could be extended to as many as 21 days if necessary. If the participant is unable to attend the baseline visit within 21-days, they will not be eligible to continue. At this visit they will complete a variety of assessments and will be provided with a 14-day supply of their usual brand cigarette to smoke between the baseline visit and the randomization visit.

4.2. Baseline Visit Procedures

Physiological measures collected and recorded on paper, and entered into REDCap at the end of the visit:

- 1. BrAC
- 2. Weight
- 3. CO
- 4. Blood Pressure (lab visit & Product evaluation)
- 5. Heart Rate (lab visit & Product evaluation)

Biological specimens collected, stored, and entered into CENIC Biosample Collection Platform:

1. Saliva sample:

Participants will be asked to provide two saliva samples during the Baseline Visit for assessment of nicotine metabolite ratio (NMR), an indicator of CYP2A6 enzyme activity. Participants must wait 30 minutes after arrival to the lab before collecting the first saliva sample. During this time, participants cannot eat, drink, chew gum or use tobacco/nicotine products. After collecting the sample, the participant is provided time to eat and/or drink and must wait another 30 minutes before collecting the second saliva sample. Samples will be stored at temperatures approximately at -20°C (UPenn) or -80°C (Wake Forest). Saliva samples will be sent regularly to be analyzed and stored at the University of Minnesota.

2. First void urine sample for smoking biomarker assessment:

Participants will be asked to bring a urine sample (first void of the day) to the Randomization Visit for biomarker assessment. Samples will be stored at temperatures approximately at -20°C (UPenn) or -80°C (Wake Forest). Urine samples will be sent regularly to be analyzed and stored at the University of Minnesota. We will assess mercapturic acids (markers of exposure to volatile organic compounds) and total nicotine equivalents (TNEs; a measure of nicotine exposure). If a participant forgets to bring his/her urine sample, then the spot urine sample will be used.

3. Spot urine sample for assessing baseline anatabine:

Participants will be asked to provide a urine sample in the lab for biomarker assessment. Samples will be stored at temperatures approximately at -20°C (UPenn) or -80°C (Wake Forest). Urine samples will be sent regularly to be analyzed for anatabine (a non-nicotine

tobacco alkaloid present in high levels in NNC and commercial but not VLNC cigarettes) and stored at the University of Minnesota.

Assessments administered via interview and entered into REDCap by the interviewer:

- 1. Concomitant Medications Form
- 2. Adverse Event Form, if needed
- 3. Health Changes Questionnaire
- 4. IVR Review of Daily Call and follow-up on missing and unusual reports and Timeline Follow-back Questionnaire (since last visit); if needed
- 5. Intention to Quit Smoking and Vaping

Assessments administered on paper and kept as a source document only:

- 4. BDI, if needed
- 5. GAD 2 week monitoring, if needed

Assessments administered directly via REDCap:

- 1. Environmental and Social Influences on Tobacco Use Questionnaire
- 2. Purchase Task: Usual Brand
- 3. Respiratory Health Questionnaire
- 4. Smoking Expectancies and Vaping Expectancies Questionnaires
- 5. Vaping Utility Questionnaire
- 6. Perceived Health Risks Questionnaire: Usual Brand

Tasks completed at baseline:

 Product evaluation: will be assessed after participants take 4 puffs of their usual brand cigarette at baseline. Following the sampling period, participants will complete the Cigarette Evaluation Scale (CES), which assesses the extent to which the product they just sampled produced various subjective effects including satisfaction, good taste, dizziness, reduced appetite, nausea, and enjoyable sensations in the throat and chest on a 7 point Likert-type scale. We will also assess changes in heart rate and blood pressure related to smoking.

4.3. Distributing Usual Brand Cigarettes

Participants will receive a supply of their usual brand cigarette to smoke between the baseline visit and the randomization visit. Participants will receive a 14-day supply and be instructed to bring their entire supply (empty packs and unused cigarettes) to the randomization visit. Participants will be notified that failure to return products throughout the study will result in removal from the study.

5. Randomization Visit

5.1. Randomization Visit Scheduling Requirements

The ideal target window between the baseline and randomization visit is 6 to 10 days. However, in rare cases, the window may be extended to as many as 21 days after the baseline visit. If the visit window is extended beyond 10 days, the participant will receive a larger supply of usual brand cigarettes (see Product Distribution section). If a participant cancels and reschedules their randomization visit outside of the 10-day window, staff will encourage the participant to return to the lab for an unanticipated visit to obtain additional product. If the participant is unable to attend the randomization visit within 21-days, they will not be eligible to continue.

5.2. Experimental Conditions

During the Randomization Visit, participants (N=480; 240 per site) will be randomized equally into one of eight experimental conditions. Participants will be assigned a cigarette that matches their menthol preference. Groups will be stratified by age and menthol status with no required sample size.

	Very Low Nicotine Cigarettes (VLNC)		Normal Nicotine Cigarettes (NNC)	
Range of Flavors	0.3% or 3mg/ml nicotine e-liquid	1.8% or 18 mg/ml nicotine e-liquid	0.3% or 3 mg/ml nicotine e-liquid	1.8% or 18 mg/ml nicotine e-liquid
Tobacco Flavors	0.3% or 3 mg/ml nicotine e-liquid	1.8% or 18 mg/ml nicotine e-liquid	0.3% or 3 mg/ml nicotine e-liquid	1.8% or 18 mg/ml nicotine e-liquid

5.3. Randomization Visit Procedures

Physiological measures collected and recorded on paper, and entered into REDCap at the end of the visit:

- 1. BrAC
- 2. Weight
- 3. CO
- 4. Blood Pressure
- 5. Heart Rate
- 6. Urine Pregnancy Test, if applicable

Biological specimens collected, stored, and entered into CENIC Biosample Collection Platform:

1. First void urine sample for smoking biomarker assessment:

Participants will be asked to bring a urine sample (first void of the day) to the Randomization Visit for biomarker assessment. Samples will be stored at temperatures approximately at -20°C (UPenn) or -80°C (Wake Forest). Urine samples will be sent regularly to be analyzed and stored at the University of Minnesota. We will assess mercapturic acids, and total nicotine equivalents (TNEs). If a participant forgets to bring his/her urine sample, then the spot urine sample will be used.

2. Spot urine sample for assessing baseline anatabine:

Participants will be asked to provide a urine sample in the lab for biomarker assessment. Samples will be stored at temperatures approximately at -20°C (UPenn) or -80°C (Wake Forest). Urine samples will be sent regularly to be analyzed and stored at the University of Minnesota.

Assessments administered via interview and entered into REDCap by the interviewer:

- 1. Concomitant Medications Form
- 2. Adverse Event Form, if applicable
- 3. Health Changes Questionnaire
- 4. IVR Review of Daily Call and follow-up on missing and unusual reports and Timeline Follow-back Questionnaire (since last visit); if needed
- 5. Intention to Quit Smoking and Vaping

Assessments administered on paper and kept as a source document only:

- 1. BDI, if applicable
- 2. GAD 2 week monitoring, if needed

Assessments administered directly via REDCap:

- 1. Respiratory Health Questionnaire
- 2. Cigarette Dependence Measures
- 3. Vaping Device Dependence Measures
- 4. Minnesota Nicotine Withdrawal Scale
- 5. Context of Product Use-Baseline
- 6. Urge to Use Questionnaire-Baseline
- 7. Perceived Health Risks Questionnaire: Study Products

If the Redcap website is not functioning, the assessments will be printed out and administered on paper. The source documents will be kept in the participant's binder. The interviewer will enter the data into Redcap when it resumes functioning properly. This information should be recorded in the 'End of Visit Evaluation Form' and entered in to REDCap.

The following tasks will be completed after participants are randomized:

1. Product evaluation will be assessed after participants take four puffs of each assigned product with a 30-second inter-puff interval, and a 15-minute inter-product interval

(Randomization, Weeks 02, 04, 08, and 12). Following each sampling period, participants will complete the *Cigarette Evaluation Scale* (CES; modified to apply to both cigarettes and vaping devices), which assesses the extent to which the product they just sampled produced various subjective effects including satisfaction, good taste, dizziness, reduced appetite, nausea, and enjoyable sensations in the throat and chest on a 7 point Likert-type scale. We will also assess changes in heart rate and blood pressure related to each product.

2. Preference Task will consist of a series of 10 choice trials, each lasting 1 minute, with a 2 minute inter-trial interval. During each trial, participants will be presented (via computer) with a choice between taking 2 puffs of the cigarette, 2 puffs of the e-cigarette, or abstaining. Indices derived from this task include: total number of cigarette puffs; total number of vaping device puffs; and total number of choices to abstain from product use.

Researchers will complete the End of Visit Evaluation Form, which will be entered into REDCap. This will allow the researcher to make note of any problems encountered during the visit and to assess the truthfulness of the participant in regard to self-report of tobacco use.

6. Experimental Phase

6.1. Study Product Distribution

The Administrative Core for the Center for the Evaluation of Nicotine in Cigarettes (CENIC) will be responsible for removing all identifying information from cigarettes received from the Research Triangle Institute (RTI), labeling each carton with a blind code, assigning product using this blind code based on the randomization schedule being provided by the CENIC Biostatistics Core, and shipping cigarettes to each site as needed based on recruitment. The site will be responsible for tracking product received and distributed to participants, collecting unused product from participants, and destroying unused open packs. The participants, investigators and study staff will not have knowledge of which product is given to a participant or whether different participants received the same or different product with regards to study cigarettes.

Between Visits 00, 01, 02, 03, and 04, participants will receive a 14-day supply of research cigarettes at each visit. Between Visits 04, 06, 08, 10, and 12, participants will receive a 28-day supply. This will ensure adequate availability of cigarettes in the numerous locations participants may typically keep a supply (home, work, vehicle, etc.) as well as avoid expending the entire supply if they miss a scheduled visit.

Additionally, participants will receive two vaping device batteries and one tank per flavor choice. Tanks are refillable, but do need to be replaced occasionally. The Administrative Core will apply a product tracking label/code to each e-liquid bottle. Product will be assigned using this code based on the randomization schedule being provided by the CENIC Biostatistics Core. Participants will receive three 10-ml e-liquid bottles at each weekly visit (Visit 00, 01, 02, 03) and six 10-ml bottles at each bi-weekly visit (Visit 04, 06, 08, 10), divided among as many as three different flavor choices. After choosing flavors, participants will fill an empty tank with each of their chosen e-liquid flavors in the lab with help of study staff. This process allows study staff to train participants on the proper

method for filling tanks. Participants will return their empty e-liquid bottles and any unused product at each weekly visit. Unopened e-liquid bottles will be considered full and all bottles with > 5 ml will be redistributed to the same participant if participants choose the same flavor in a future week. If a participant loses their vaping device or e-liquids, we will provide replacements up to two times. If a participant loses their device or liquids more than twice, we may withdraw them from the study. When participants are provided with their study vaping device for the first time, they will be told that losing their device or e-liquids multiple times may result in study withdrawal.

If there is prior knowledge a participant will be missing a visit (e.g., planned vacation, laboratory closure, etc.), or a participant is unable to attend the randomization visit within the 10-day window, then the participant will be provided with an adequate supply of study product until their next visit. The participant will be given a 21-day supply of cigarettes if they will miss Visit 01, 02 or 03 or if the randomization visit is between 11 and 17 days from screening, a 28-day supply of cigarettes if they will miss Visit 04 or the randomization visit is 18 or more days from screening, and a 35-day supply of cigarettes if they will miss Visit 06, 08 or 10. For e-liquids, participant will be given 5 bottles (10 ml each) if they will miss Visit 01, 02 or 03, 6 bottles if they will miss Visit 04, and 8 bottles if they will miss Visit 06, 08 or 10. In addition, participants can come to the laboratory during normal business hours to receive additional study product if needed.

6.2. Study Product Accountability

Participants will be required to keep track of the vaping device, tanks, and all the cigarettes and eliquid provided to them. They will be instructed to return all unused cigarettes and empty cigarette packs and vaping device, tanks, and e-liquid bottles each week. Because participants are provided with an ample supply of research cigarettes and e-liquid (to account for unanticipated missed visits or greater than anticipated use), they will be expected to return unused product at each visit to remain enrolled in the study.

Research staff will complete the 'Product Accountability Log' directly in REDCap. Any discrepancies in the product dispensed versus product returned will be discussed and recorded in the log. Empty cigarette packs and/or empty bottles will be saved. Unused cigarettes or bottles will be redistributed to the participants during Visits 01-12. At Visit 10, participants will be made aware that they will be required to turn in all study products (cigarettes and vaping devices) at Visit 12.

During the Experimental Phase, if participants lose cigarettes or e-liquids and require an unscheduled visit to the laboratory to supplement their supply, they will be told the next time they lose their supply of either product they will have to wait until their next scheduled appointment to receive more product.

6.3. Experimental Phase Visit Scheduling Requirements

A computer-generated ideal visit calendar will automatically generate the ideal visit windows once the participant has been randomized. If a participant misses a visit and is not able to reschedule during the window, that visit will not be 'made-up' in the future. All measures that were not completed will be considered missing data and will not be collected during future visits. If a visit mistakenly occurs outside of the designated window, this is a protocol deviation. A 'Protocol Deviation Form'

will need to be completed and tracked in REDCap. If a participant is not able to attend Visit 12, then it should be rescheduled even if it is outside of the scheduling window. This will be documented as a protocol deviation. Participants that do not attend scheduled lab visits, miss daily IVR phone calls, and do not respond to phone messages will be considered lost to follow-up. A certified letter will be sent to notify them as defined by the site's Standard Operating Procedure (SOP).

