6.4. Visit 01, 02, 03, 04, 06, 08, 10, and 12 Procedures

Physiological measures collected and recorded on paper, and entered into REDCap at the end of the visit:

- 1. BrAC
- 2. Weight
- 3. CO
- 4. Blood Pressure
- 5. Heart Rate
- 6. Urine toxicology assessment (Visit 12 only)
- 7. Pregnancy test (if applicable, Visits 4, 8, 12 only)

Biological specimens collected, stored, and entered into CENIC Biosamples Collection Platform:

1. First void urine sample for smoking biomarker assessment (Visits 4, 8, 12):

Participants will be asked to bring a urine sample (first void of the day) for biomarker assessment. Samples will be stored at temperatures approximately at -20°C (UPenn) or -80°C (Wake Forest). Urine samples will be sent regularly to be analyzed and stored at the University of Minnesota. We will assess mercapturic acids, and total nicotine equivalents (TNEs). If a participant forgets to bring his/her urine sample, then the spot urine sample will be used.

2. Spot urine sample for assessing baseline anatabine:

Participants will be asked to provide a urine sample in the lab for biomarker assessment. Samples will be stored at temperatures approximately at --20°C (UPenn) or -80°C (Wake Forest). Urine samples will be sent regularly to be analyzed and stored at the University of Minnesota.

Assessments administered via interview and entered into REDCap by the interviewer:

- 1. Concomitant Medications
- 2. Adverse Event Form, if applicable
- 3. Health Changes Questionnaire
- 4. IVR Review of Daily Call and follow-up on missing and unusual reports and Timeline Follow-back Questionnaire; if needed
- 5. Intention to Quit Smoking and Vaping
- 6. Drug Use Questionnaire, 1 month version (Visits 4, 8, 12)

Assessments administered on paper and kept as a source document only:

- 1. BDI, if applicable
- 2. GAD 2 week monitoring, if needed

Assessments administered directly via REDCap:

- 1. Respiratory Health Questionnaire
- 2. MNWS
- 3. Urge to Use Questionnaire-Experimental
- 4. Perceived Health Risks Questionnaire: Study Products (Visits 2, 4, 8, 12)
- 5. CESD (Visits 4, 8, 12)
- 6. Alcohol Use Questionnaire, 1 month version (Visits 4, 8, 12)
- 7. Context of Product Use-Experimental Version (Visits 4, 8, 12)
- 8. Smoking Stages of Change (Visits 4, 8, 12)
- 9. Cigarette and Vaping Dependence Questionnaires (Visits 4, 8, 12)
- 10. Purchase task-Study Cigarette + Vape Version (Visit 12)
- 11. Smoking and Vaping Expectancies Questionnaires (Visit 12)

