8.2. Early Termination

If a participant decides to withdraw from the study prior to completion or if they are withdrawn by the PI or LMM due to safety concerns, they will be scheduled for an early termination visit. If the participant is seen within the window of a regularly scheduled visit, all measures for that visit will be collected. Additional questionnaires and safety measures may be obtained (urine sample for biomarkers and pregnancy screen, CES-D, and BDI-II if appropriate) if not scheduled during the normal visit. If the subject is seen outside of a regularly scheduled visit window, the following measures will be obtained:

Physiological measures collected and recorded on paper, and entered into REDCap at the end of the visit:

- 1. BrAC
- 2. Weight
- 3. CO
- 4. Blood Pressure
- 5. Heart Rate
- 6. Pregnancy test (if applicable)

Biological specimens collected, stored, and entered into CENIC Biosample Collection Platform:

- 1. Spot urine sample for assessing baseline anatabine:
 - Participants will be asked to provide a urine sample in the lab for biomarker assessment. Samples will be stored at temperatures approximately at -20°C (UPenn) or -80°C (Wake Forest). Urine samples will be sent regularly to be analyzed and stored at the University of Minnesota.
- 4. First void urine sample for smoking biomarker assessment. Participants will be asked to bring a sample (first void urine of the day) for biomarker assessment. Samples will be stored at temperatures approximately at -20°C (UPenn) or -80°C (Wake Forest). Urine samples will be send quarterly to be analyzed and stored at the University of Minnesota. Total nicotine equivalents and mercapturic acids will be assessed. If a participant forgets to bring his/her urine sample, then the spot urine sample will be used.

Assessments administered via interview and entered into REDCap by the interviewer:

- 1. Concomitant Medications
- 2. Adverse Event Form, if applicable
- 3. Health Changes Questionnaire
- 4. IVR Review of Daily Call and follow-up on missing and unusual reports and Timeline Follow-back Questionnaire; if needed
- 5. Intention to Quit Smoking and Vaping
- 6. Drug Use Questionnaire, 1 month version

Assessments administered on paper and kept as a source document only:

- 1. BDI, if applicable
- 2. GAD 2 week monitoring, if needed

Assessments administered directly via REDCap:

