- 12. Smoking and oral contraceptives in women: Women who smoke and are over the age of 35 should not take oral contraceptives that contain estrogen without consulting their physician. Smoking while using oral contraceptives can increase the risk of having a cardiovascular event such as a heart attack or stroke. Additionally, there is a potential risk of thrombosis associated with hormonal therapy (including contraceptives) and smoking.
- 13. Smoking and medications: Quitting smoking can greatly benefit participants' health. However, changes in smoking can lead to changes in how well some medications work. Participants should disclose all medications they are taking. We also recommend that participants discuss any planned or actual changes in how much they smoke with their doctor, especially if they are taking any medications for psychiatric, cardiovascular, or other serious diseases.
- 14. Unforeseen risks: There may be additional unforeseen short and long-term risks of participation.

18. Avoiding Risks to Fetus

If participants choose to be sexually active, they are advised to use an appropriate "double barrier" method of birth control (such as female use of a diaphragm, intrauterine device (IUD), or contraceptive sponge, in addition to male use of a condom) or the female should be using prescribed "birth control" pills, injections, or implants. Female participants with child-bearing potential will be tested for pregnancy at Screening, Randomization, and Visits 04, 08 and 12. If a participant becomes pregnant during the study, she will be withdrawn from the study. Approximately 30 days after being withdrawn or having a positive pregnancy test at Visit 12, the research staff will call the participant to confirm her due date. The licensed medical monitor will follow-up with the participant after delivery to ask questions about the baby's health.

19. Expected benefits of participation

There are no immediate benefits from participating in the study. The information obtained from this study may ultimately help the Food and Drug Administration decide how best to regulate tobacco products with the goal of improving public health.

20. Suicidality/Mental Health Monitoring

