Participants who make any response other than "not at all" on the suicidal ideation question of the Prime MD (Question 1i), indicate suicidal ideation, have attempted suicide in the past month, or have had a suicide attempted in the past 5 years on the MlNI suicide subscale will not be eligible to participate in the study. If the participant has attempted suicide between 6-10 years ago, then the LMM must approve eligibility. To determine if a participant is in immediate danger, staff will ask the participant two questions to determine level of risk: "Are you feeling suicidal?" and "Do you have a plan to kill yourself today?" If the participant has a plan to kill himself/herself, staff will put the participant in contact with the suicide prevention hotline (Durham Center Crisis Line at [name]; Philadelphia Suicide Prevention [contact] or UPenn's HELP line: [name]). If the participant refuses to talk to the hotline and leaves, the study staff will call 911. They will also contact the Study Coordinator and Site PI to inform them of the situation as soon as possible. If the participant does not have a plan to kill himself/herself, the study staff will recommend he/she speaks with the suicide hotline. The visit will continue as normal, but the participant will not be eligible for the study. The participant will be paid \$30 and provided with local mental health resources. The on-site clinician will be available by phone for consultation within 24-hours.

Additionally, any participant whose score on the Prime MD indicates Major Depressive Disorder will be administered the Beck Depression Inventory (BDI) and the GAD 2 week monitoring on paper. The BDI will be submitted, along with the Prime MD, Brief Medical History Questionnaire, Brief Medical History Follow-up Questionnaire, and the MINI suicide subscale to the licensed medical monitor for eligibility review. If he/she determines a participant with Major Depressive Disorder is eligible for study participation, the participant will complete the BDI each visit to monitor changes in his/her mood.

21. Adverse Events (AE)

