21.1. Identifying Adverse Events

While participating in the trial, adverse events and concomitant medications will be assessed at every study visit and vital signs and carbon monoxide will be measured. Adverse events will typically be identified during the administration of the Health Changes Questionnaire and Respiratory Health Questionnaire, and in some cases during the administration of the CESD. Other events may be identified from physiological study measures or by spontaneous reports during non-scheduled assessments. The medical monitor is notified about all AEs within 10 days.

Questionnaire items that will be reviewed:

- 1. Health Changes Questionnaire
 - 1. Have you had any negative changes in your physical or mental health since your last visit? If yes, briefly describe.
 - 2. Since your last visit, have you received any form of medical care? If yes, briefly describe.

No new AE report will be required if one or more conditions below are met and the description does not otherwise meet the definition of an AE.

- a. Existing AE already open for reported symptom
- b. Pre-existing condition without increase in severity or frequency of symptoms (brief medical history will be updated if not previously reported).
- c. Nicotine withdrawal symptoms that don't meet AE criteria
 - A. The following withdrawal symptoms are considered expected withdrawal symptoms and are not considered AEs
 - 1. Desire or craving to smoke
 - 2. Restlessness
 - 3. Impatience
 - 4. Increased appetite, hunger, weight gain*

*If a participant indicates any clinical behaviors such as binging or purging this should be recorded as an Adverse Event and the PrimeMD should be completed.

- B. The following withdrawal symptoms would be considered an AE if the participant indicated the symptom had a significant impact on your daily life, caused a major disruption of functioning, or took any medication for it.
 - 1. Anger, irritability, frustration
 - 2. Difficulty Concentrating
 - 3. Insomnia
 - 4. Nightmare/Night Terrors
 - 5. Depressed (sad) mood*
 - 6. Anxious (nervous) mood*

*If a depressed (sad) mood and an anxious (nervous) mood AE is reported, the participant will complete the Prime MD and be assessed for suicidality.

- d. Received preventative or follow-up medical care.
- e. Other (explain).

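### The no-make-up rule in section 6.3 has no safety exception, so missing Visit 04 or Visit 08 doubles the on-product interval without a pregnancy test or CES-D from 4 to 8 weeks

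*Combined protocol and SAP*

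**What the plan says.** Section 6.3 (Experimental Phase Visit Scheduling Requirements) does not allow a visit to be made up once it has been missed and cannot be rescheduled within its window. On the content of that visit it says: "All measures that were not completed will be considered missing data and will not be collected during future visits". It makes one exception. If Visit 12 cannot be attended, "then it should be rescheduled even if it is outside of the scheduling window".

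Section 6.4 places both the pregnancy test (where applicable) and the CES-D at Visits 04, 08 and 12 only. Section 18 and the procedures table in section 32 agree. Before product use, the pregnancy test is done at Screening and Randomization; the CES-D is done at Screening but not at Randomization.

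Product is supplied across a missed visit. For a known absence, section 6.1 provides "a 28-day supply of cigarettes if they will miss Visit 04", together with six bottles of e-liquid. For a missed Visit 08 it provides 35 days of cigarettes and eight bottles.

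On the consequence of pregnancy, section 18 says: "If a participant becomes pregnant during the study, she will be withdrawn from the study". Under section 21.1, a CES-D score of 16 or higher opens an adverse event form and brings in the medical monitor, for anyone not already followed for depression. Section 28.4 lists change in CES-D as a safety outcome.

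Section 8.2 (Early Termination) allows a pregnancy screen and a CES-D to be added when they are not part of that visit's schedule, and describes the additions as questionnaires and safety measures.

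**The concern.** Refusing make-up collection is sensible for measures tied to a study week. Applied to safety checks, it withholds a check from someone who is in the clinic and still receiving product.

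The pregnancy test is the main gap. The protocol requires withdrawal on pregnancy, and the test is its only scheduled means of finding a pregnancy that the participant does not know about. Health questions cannot detect that. Under the rule as written, a participant who missed Visit 04 and attends Visit 06 gives a spot urine sample, receives a further 28-day cigarette supply and six e-liquid bottles, and is not tested until Visit 08.

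The CES-D gap is narrower. What is lost is the score threshold that opens an adverse event form for people not already monitored, along with one dated observation on a listed safety outcome.

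The rule also sits awkwardly beside section 8.2, which permits both measures off schedule for people leaving the study. Section 6.3 does not permit them for people who stay on product.

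**Working it through.** **Inputs.** Nominal days from the timeline in section 2.1: Screening 0, Randomization 14, Week 4 = 42, Week 6 = 56, Week 8 = 70, Week 10 = 84, Week 12 = 98. Assessment schedule from sections 6.4, 18 and 32.

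**Formula.** Interval = day of the next test minus day of the previous test. Product use starts at Randomization, day 14.

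**Plan's own interval, reproduced.** 42 − 14 = 28, 70 − 42 = 28 and 98 − 70 = 28 days, so 4 weeks between pregnancy tests on schedule.

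**Pregnancy test, longest on-product interval.** The last column assumes that the missed test is done at the next scheduled visit and that this visit is attended.

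| Missed | As written | Tested at next visit |
|---|---|---|
| None | 28 days | 28 days |
| Visit 04 | 70 − 14 = 56 days | 56 − 14 = 42 days (Visit 06) |
| Visit 08 | 98 − 42 = 56 days | 84 − 42 = 42 days (Visit 10) |
| Both | 98 − 14 = 84 days | 42 days |

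In the last row, the tests fall at Visits 06, 10 and 12: 56 − 14 = 42, 84 − 56 = 28 and 98 − 84 = 14 days, so the longest is 42.

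Delay relative to schedule: 56 − 28 = 28 days for one miss and 84 − 28 = 56 days for two.

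Part of that delay that the change removes: 56 − 42 = 14 days for one miss and 84 − 42 = 42 days for two.

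**CES-D.** Counted as time on product, the longest intervals are the same: 4, 8, 8 and 12 weeks. Counted between actual administrations, they are longer whenever the first interval is involved, because the previous CES-D is at Screening (day 0):

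- on schedule, 42 days (6 weeks);
- Visit 04 missed, 70 days (10 weeks), or 56 days with the change;
- Visit 08 missed, 98 − 42 = 56 days (8 weeks), or 84 − 42 = 42 days with the change;
- both missed, 98 days (14 weeks), or 56 days with the change.

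**Does product really continue?** For a foreseen absence, section 6.1 answers directly. For an unforeseen miss of Visit 08, the 28-day cigarette supply from Visit 06 covers day 56 to day 84, which is Visit 10. For an unforeseen miss of Visit 04, the 14-day supply from Visit 03 (day 35) would have to last 56 − 35 = 21 days at full use. Section 6.2 says the supply is made ample partly to cover unanticipated missed visits, and section 6.1 lets participants collect more during business hours.

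**Does the plan tolerate such misses?** Under section 15 the completion bonus survives two missed visits between Visits 01 and 08 if Visits 10 and 12 are attended. A participant who misses both 04 and 08 can therefore still qualify.

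**The case against.** The strongest reply is that section 6.3 is a scheduling and data rule and does not forbid a clinically indicated test. The protocol has codes for additional visits (section 31), accepts adverse events reported at non-scheduled assessments (section 21.1), and lets the medical monitor or investigator discontinue a participant for safety (section 22). That is fair as far as it goes. None of these provisions orders the missed test, though, and a site following section 6.3 literally would not do it.

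Second, the avoidable delay is modest: 2 weeks after a single miss. The 6-week gain needs both Visits 04 and 08 missed with Visits 06 and 10 attended. No document sets a maximum acceptable test interval. This stands, and it limits the weight of the point.

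Third, other protections exist. Pregnancy, trying to conceive and refusing adequate protection are exclusions; contraception advice is given; attendance is paid; and participants already smoke daily, so the issue is continued provision and delayed withdrawal rather than first exposure. These lower the likelihood or the added harm but do not detect an unrecognised pregnancy.

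Fourth, mood is still monitored. Each attended visit asks "Have you had any negative changes in your physical or mental health since your last visit". A reported depressed or anxious mood event leads to the Prime MD and a suicidality assessment. For those enrolled with Major Depressive Disorder, section 20 says "the participant will complete the BDI each visit to monitor changes in his/her mood". This stands, and is why the CES-D gap is only partial.

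Fifth, early termination is a last contact, whereas a continuing participant has later scheduled tests. That explains the difference in section 8.2, but not why a test should be withheld at Visit 06 or 10.

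Finally, a late CES-D does not fill the missing Week 4 or Week 8 value. That is correct. It adds a dated safety observation only.

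**Conclusion.** The concern holds. As written, missing Visit 04 or Visit 08 lengthens the on-product pregnancy-test interval from 28 to 56 days, and missing both lengthens it to 84 days. An unrecognised pregnancy could continue on study product for up to 4 more weeks, or 8 more if both visits are missed, before the next scheduled test. Testing at the next attended visit would hold the interval to 42 days. The CES-D shows the same on-product intervals, with a smaller consequence.

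This rests on the nominal timeline, which the protocol says may vary; the widths of the experimental-phase windows are not given, and a visit rescheduled inside its window is not missed. It also rests on reading section 6.3 literally. The number of participants affected cannot be derived. The change is recommended because it is cheap and closes a safety gap. It does not affect the primary analysis.

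**What to change.** Limit the no-make-up rule in section 6.3 to non-safety measures. Add a sentence saying that a pregnancy test (where applicable) or CES-D missed at Visit 04 or 08 is done at the next attended visit and recorded with its actual date. Use make-up CES-D scores for safety monitoring, including the threshold of 16, and analyse them by actual date rather than as Week 4 or Week 8 values.

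The cost is a one-sentence amendment and, per missed visit, one test on urine already being collected and one 20-item questionnaire at a visit the participant is attending anyway. The only drawback is that some CES-D values will fall at Week 6 or Week 10.
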